10.2.2 Assessment of Severity

Adverse events will be categorized as 1=mild, 2= moderate, 3=severe, 4=life-threatening, 5= death.

10.3 Documentation

10.3.1 Serious Adverse Events (SAE)

The sponsor's SOPs provide more detail on safety reporting.

During the entire duration of the study all serious adverse events (SAEs) are collected, fully investigated and documented in source documents and electronic case report forms (eCRF). Study duration encompassed the time from when the participant signs the informed consent until the final examination.

10.3.2 Adverse Events (AE)

The following information needs to be collected for adverse events:

- time of onset,
- duration,
- resolution,
- action to be taken,
- assessment of intensity, and
- relationship with study treatment.

For assessment of safety outcomes see

chapters 9.3

10.4 Reporting of serious adverse events (SAE) and other safety related events

10.4.1 Reporting of SAEs

All SAEs must be reported immediately and within a maximum of 24 hours to the sponsor-investigator of the study. The sponsor-investigator will re-evaluate the SAE and return the form to the site.

SAEs resulting in death are reported to the EKNZ within 7 days.

10.4.2 Reporting of SUSARs

A SUSAR needs to be reported to the CEC (EKNZ) and to the CA (Swissmedic) (via Sponsor-Investigator) within 7 days, if the event is fatal, or within 15 days (all other events).

10.4.3 Reporting of safety signals

All suspected new risks and relevant new aspects of known adverse reactions that require safety-related measures, i.e. so called safety signals, must be reported to the sponsor-investigator within 24 hours. The sponsor-investigator must report the safety signals within 7 days to the CEC (EKNZ) and to the CA (Swissmedic).

10.4.4 Reporting and handling of pregnancies

Pregnant participants must be withdrawn immediately from the clinical study. Any pregnancy during the treatment phase of the study and within 30 days after discontinuation of study medication will be reported to the Sponsor-Investigator within 24 hours.

The course and outcome of the pregnancy will be followed up until the end of the first trimenon, and any abnormal outcome regarding the mother or the child be documented and reported. For further information see Chapter 7.5.

10.4.5 Periodic reporting of safety

An annual safety report is submitted once a year to the local Ethics Committee via BASEC and to the CA via sponsor-investigator.

10.4.6 Follow-up of (Serious) Adverse Events (AE)

In case of minor health problems the participant will have to stay under medical control in our department.

In case of major health problems the participant will be transferred to the emergency department in the University Hospital of Basel (USB). The responsible investigator will inform the health care provider about the participation in the study. For unblinding see 6.3.

Information about the outcome in all above-mentioned cases will be collected until full recovery.

11 STATISTICAL METHODS

11.1 Hypothesis

Fampridine improves working memory performance in healthy humans.

11.2 Determination of Sample Size

We are interested to detect a drug effect with at least medium effect size. The estimation of N=44 is based on a power analysis using dependent two-tailed t-tests assuming to detect a medium effect size (Cohens $dz = 0.5$) with a power of 90% at $\alpha=0.05$ (software: G-power 3).

11.3 Statistical criteria of termination of trial

As soon as 44 participants will have completed the entire study. For subjects still enrolled at that time point see 11.4.1.

11.4 Planned Analyses

All analyses will be performed with the software R. The differences between the experimental conditions (placebo, verum) will be analyzed using linear mixed models in combination with analysis of variance (SS II). Subjects will be included as the random effect of the mixed model. Sex and age will be inserted as covariates.

In case of significant interactions between covariates and experimental condition, post-hoc tests will be applied to describe the interaction.

To control for an influence of other variables, possible confounders will be entered into the model as covariate (each possible confounder entering the statistical analyses separately and corrected for multiple comparisons with the Bonferroni method).

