6 STUDY DESIGN

6.1 General study design and justification of design

Pharmacological proof-of-concept study on the effects of 10 mg fampridine (twice daily oral administration) on physiological processes, in particular working memory, in healthy participants using the following design:

- randomized
- double-blind (participant, study team)
- placebo-controlled
- cross-over
- counter-balanced

The duration of the study from first participant in to last participant out is approx. 24 months. Duration for an individual study participant will be at most 7 to max. 15 weeks, depending on the duration of the wash out period.

There will be two intervention periods of 3.5 days during which medication (fampridine /placebo) will be applied separated by a wash out period of 8 (days between Visit 3 and Visit 4; equivaling over 30 half-lives of the study drug) up to 82 days (12 weeks).

Two test days will take place during each intervention period: one on the first day and one on the last day of each period during which cognitive functions under the influence of fampridine/placebo will be assessed using parallel versions of tests.

At the beginning of test day 1 (visit 2), each subject will be randomized to receive either placebo or fampridine first.

After the administration of study medication (visits 2-5) there will be a 4-h waiting period allowing the medication to reach peak cerebrospinal fluid levels (Hayes 2004). After this time period, the cognitive test battery will be administered.

At the end of each visit, participants will be asked about their actual wellbeing. If there are no complaints or symptoms, participants can be dismissed. In case of minor health problems, the participant will have to stay in the study center until recovery under medical supervision. In case of more severe incidents staff acts according to chapter 10.4.6.

The study will end for the subjects in the evening of the second test day of the second intervention period (visit 5). The duration for the different study parts see table 1 (Duration of Study parts, page 12).

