6.2.1 Randomization

After pre-examination on visit 2, each participant will be assigned to a randomization number. Each eligible participant will be allocated to one of the two randomization groups (Placebo/Verum or Verum/Placebo) according to the maximum tolerated imbalance (MTI) procedures. This allocation will be generated automatically by secuTrial®. This procedure ensures that participants will be randomly allocated to the two groups, while accounting for sex as a covariate of potential importance.

The replacement of all Drop-Outs will be carried out after assignment of all 44 medication kits is completed. There will be replacement of Drop-Outs until data of approximately 44 participants are completed.

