7 STUDY POPULATION

7.1 Eligibility criteria

Participants fulfilling all of the following inclusion criteria are eligible for the study:

- male or female
- generally healthy
- normotensive (BP between 90/60mmHg and 140/90mmHg)
- BMI between 19 and 29,9 kg/m²
- aged between 18 and 30 years
- fluent German-speaking
- IC as documented by signature
- At least double vaccination against Covid-19

The presence of any one of the following exclusion criteria will lead to exclusion of the participant:

- contraindications to the class of drugs under study, e.g. known hypersensitivity or allergy to 4-aminopyridine
- use of potassium channel blockers within the last 3 months
- concomitant treatment with OCT 2 inhibitors and -substrates (e.g. cimetidine, propranolol)
- acute or chronic psychiatric disorder (e.g. major depression, psychosis, somatoform disorder, suicidal tendency)
- acute cerebrovascular condition
- history of seizures
- risk of lowered seizure threshold (due to e.g. sleep deprivation, withdrawal of alcohol after alcohol abuse)
- renal impairment
- history of malignant cancers
- walking problems (e.g. due to dizziness)
- other clinically significant concomitant disease states (e.g. hepatic dysfunction, cardiovascular disease, diabetes, asthma,
- bradycardia < 50/min during clinical examination
- clinically significant laboratory or ECG abnormality that could be a safety issue in the study
- known or suspected non-compliance (e.g. missing more than one dose of study medication per intervention phase)
- drug or alcohol abuse
- inability to follow the procedures of the study, e.g. due to language or psychological problems of the participant
- participation in another study with an investigational drug within the 30 days preceding and during the present study
- prior participation (less than two years ago) in a study investigating working memory (notably the n-back task)
- enrolment of the investigator, his/her family members, employees and other dependent persons
- smoking (>3 cigarettes per day)
- intake of psychoactive drugs (e.g. benzodiazepines, antidepressants, neuroleptics)
- pregnancy or breast feeding
- experiencing a syncope during basal rMT measuring

Exclusion Criteria concerning TMS measurement

- metal in the brain, skull or elsewhere in the body (e.g., splinters, fragments, clips, etc.)
- implanted neurostimulator (e.g., DBS, epidural/subdural, VNS)
- cardiac pacemaker or intracardiac lines
- medication infusion device

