9.2 Assessments of outcomes

9.2.1 Assessment of primary outcome

- High-load working memory performance will be measured as follows: We will use the letter n-back task (Heck, Fastenrath et al. 2014) which includes a 3-back task assessing working memory. The 3-back task requires participants to respond to a letter repeat with two intervening letters (for example, S-m-b-s-g...). Performance will be quantified with the d' measure controlling for false positives. We will use parallel versions (different sequences) for the four test days. Primary outcome will be performance after repeated intake of study medication.

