11.4.1 Datasets to be analyzed, analysis populations

We will apply a Per-Protocol-Analysis, i.e. the analysis of the primary and secondary outcome measures will be only performed with those participants, who completed all tests and investigations. There will be replacement of Drop-Outs until data of 44 participants are completed. Drop-Outs will be thoroughly described to assess the reason(s) for dropping out.

We will recruit up to 4 subjects more towards the end of the trial to prevent under-recruitment due to Drop-Outs. If more than 44 subjects will complete all tests and investigations their data will also be analyzed.

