11.4.2 Analysis for the primary outcome

A significance level of $p < 0.05$ will be considered as significant.

The dependent variable is the primary outcome (i.e. 3-back (d')) after repeated administration of study medication). The independent variable of interest is the experimental condition (placebo or verum).

To control for possible confounders or moderators, we will also consider tiredness, motivation, headache, gastrointestinal discomfort, dizziness, mood as assessed by MADRS-S, potassium blood concentration at screening, body weight, duration of washout period and vital signs as covariates (each covariate entering the statistical analysis separately). In case of a significant (i.e. after Bonferroni correction for multiple comparisons) interaction between independent variables of interest and covariates, post-hoc analysis will be applied to describe the interaction effect.

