11.4.3 Analyses for secondary outcomes

Behavioral secondary outcomes will be treated statistically the same way as the primary outcome, but a Bonferroni correction (i.e. corrected for the number of behavioral secondary outcomes) will apply separately for the main effect (i.e. drug vs. placebo) and the interaction effect (i.e. main effect x acute vs. repeated administration). In the case of a significant (i.e. Bonferroni-corrected) interaction effect, post-hoc analysis will be applied to describe the interaction effect.

The measure of the non-behavioral secondary outcome (i.e. rMT) will be treated statistically the same way as the primary outcome measure.

11.4.4 *Interim analyses*

No interim analyses are planned.

11.4.5 *Safety analysis*

Safety data will be analyzed for all participants, who received at least one dose of study medication.

11.4.6 *Deviation(s) from the original statistical plan*

Deviations from the original statistical plan will be justified and reported to the ethical committee and regulatory authorities.

Deviation from the original statistical plan will be performed, if reviewers demand specific analyses. If in the meantime other studies find important effects or confounding effects related to our study, we will include these found confounders (if we have assessed those) as an additional analysis in our statistical plan beside our planned analyses.

11.4.7 *Handling of missing data and drop-outs*

Missing data will be recorded as NA.

Drop-Outs see chapter 11.4.1.

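### The cross-over model has no period term; adding one costs one degree of freedom and protects precision, and the drug estimate too if completers end unequal by sequence

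*Combined protocol and SAP*

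**What the plan says.** The trial is a two-sequence, two-period cross-over, described in section 6.1 as counter-balanced. On testing, that section says: "Two test days will take place during each intervention period: one on the first day and one on the last day of each period". The primary outcome (section 5.1) is 3-back d' after repeated intake, so each participant gives one value per period, at visits 3 and 5.

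The model is in section 11.4: a linear mixed model for placebo against verum. "Subjects will be included as the random effect of the mixed model. Sex and age will be inserted as covariates". Section 11.4.2 names condition as the independent variable of interest and lists further covariates, entered one at a time: tiredness, motivation, three side-effect ratings, MADRS-S, potassium, body weight, wash-out duration and vital signs. Section 11.4.3 adds acute versus repeated administration for the behavioural secondary outcomes, which is the visit within a period and not the period itself. It gives rMT the same treatment as the primary outcome. Period, sequence and visit order are not named.

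The design does guard against order and practice. Section 7.1 excludes people who took part in a working-memory study, n-back in particular, within the last two years. Section 9.2.1 says "We will use parallel versions (different sequences) for the four test days".

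On who ends up in each sequence, section 6.2.1 uses a maximum tolerated imbalance procedure without stating its limit, and says "The replacement of all Drop-Outs will be carried out after assignment of all 44 medication kits is completed". Section 11.4.1 analyses completers only, allows up to 4 extra recruits, and says "If more than 44 subjects will complete all tests and investigations their data will also be analyzed".

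**The concern.** The design treats order as something to control, but the analysis leaves it out. If d' moves generally between visit 3 and visit 5, each paired difference (fampridine minus placebo) is pushed up for those who take fampridine second and down for those who take it first.

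With equal sequences the pushes cancel in the mean but stay in the spread. The standard error is then too large and the test conservative. With unequal sequences the mean shifts as well.

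The terms already in the model do not deal with this. Sex, age and wash-out duration are constant within a participant, so as main effects they cannot absorb a change between that participant's two visits. The ratings and vital signs vary by visit, but they would pick up a period shift only as far as they happen to track it. Parallel versions change the items and do not rule out general practice.

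**Working it through.** **Inputs.** From section 11.2: dz = 0.5, two-tailed dependent t-test, alpha 0.05, power 90%, N = 44. From section 11.4.1: 44 completers and up to 4 extra. *Assumed:* the period effect δ (second period minus first), in SDs of the paired difference, range 0.25 to 1.0. The completer splits are also illustrative, because no drop-out rate and no imbalance limit are given.

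**1. The plan's own figure.** Noncentral t with noncentrality 0.5·√N and N − 1 df gives 0.8930 at N = 43 and 0.9000 at N = 44. The stated 44 is reproduced.

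**2. Cost of the term if there is no period effect.** Residual df are 88 values − 44 subjects − 1 for condition = 43, and 42 with period. The critical t goes from 2.0167 to 2.0181. With period in the model the noncentrality is 0.5·√(4·n1·n2/N) on N − 2 df. Power is 0.8997 at 22/22, 0.8973 at 24/20 and 0.8943 at 25/19, against 0.9000 without the term.

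**3. Omitting the term, 22/22 completers.** Paired differences are 0.5 ± δ plus normal error. The estimate is unbiased. Section 11.2 does not say whether the SD behind dz contains period variance, so both readings are shown.

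*Reading A: dz excludes period variance (error SD 1).* The standard error is inflated by √(1 + δ²·44/43).

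| δ | SE ratio | Power without | Type I without | Power with |
|---|---|---|---|---|
| 0.25 | 1.03 | 88.9% | 4.3% | 90% |
| 0.5 | 1.12 | 85.1% | 2.8% | 90% |
| 1.0 | 1.42 | 67.2% | 0.6% | 90% |

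*Reading B: dz already includes it (error SD √(1 − δ²), total SD 1).* Without the term, power is 90.6% at δ = 0.25 and 92.9% at δ = 0.5. With it, the effective dz is 0.5/√0.9375 = 0.516 and 0.5/√0.75 = 0.577, and power is about 92% and 96%. δ = 1.0 has no counterpart here, because the error SD would be zero.

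**4. Unequal completers.** The estimate without the term shifts by δ·(n1 − n2)/N, where n1 is the number taking fampridine second. For 24/20 at δ = 0.5: 0.5 × 4/44 = 0.045. Power below is at δ = 0.5, helpful / unhelpful direction, to about one point.

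| Split | Shift, δ = 0.25 | Shift, δ = 0.5 | A without | A with | B without | B with |
|---|---|---|---|---|---|---|
| 24/20 | 0.023 | 0.045 | 91 / 77% | 90% | 96 / 87% | 96% |
| 25/19 | 0.034 | 0.068 | 93 / 73% | 89% | 98 / 83% | 96% |
| 26/22 (N = 48) | 0.021 | 0.042 | 93 / 82% | 92% | 97 / 91% | 97% |

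Type I error without the term stays at or below 5% in all these cases. At the more extreme 26/18 it reaches about 6%, for δ from 0.5 to 1.0 under reading A.

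**5. Check in the mixed model itself.** This used 60 simulated data sets at 25/19, δ = 0.5 and true effect 0.5. Condition + sex + age gave a mean estimate of 0.550 and SE 0.166. Adding wash-out duration as a main effect changed neither. Adding period gave 0.484 and 0.151. The gap of 0.066 agrees with the 0.068 from the formula.

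**The case against.** The strongest reply is that the planned test is valid and the loss may be small.

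- **Reading of dz.** In a dependent t-test dz is naturally the mean over the SD of the raw differences, which in a counter-balanced cross-over already contains any period shift. That is reading B, under which the stated 90% is kept. At δ = 1.0, reading A amounts to a raw dz of about 0.5/1.42 = 0.35, a smaller effect than section 11.2 plans for. This stands: the 67% figure should not be taken as the expected power. But dz = 0.5 is a conventional medium effect with no variance source given, so reading A cannot be excluded, and the term gains power under B too.
- **No evidence of a period effect.** The exclusion and the parallel versions are precautions, and visit 3 is already a second n-back session. This stands. The omission is certain; the size of its consequence is not.
- **Allocation limits imbalance.** Section 6.2.1 sends each eligible participant through the same procedure, which would include replacements and extras. This stands for assignment. It does not fix the split among completers, and no rule makes a replacement take the drop-out's sequence.
- **The shift is small.** At 0.021 to 0.068 SD it is under half a standard error (about 0.15). This stands. It averages to zero over randomisation, but not within the one trial that is run.
- **Secondary outcomes.** All power figures concern the two-value primary model; none was computed for the four-visit behavioural models, and no practice effect on rMT is claimed. The case for those models is consistency with section 11.4.3.

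**Conclusion.** The concern holds. The model names no period, visit or sequence term, and nothing else in the plan takes a visit 3 to visit 5 shift out of the within-subject error or secures equal sequences among completers.

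This is a loss of efficiency, with a modest conditional shift added if sequences are unequal. It does not invalidate the trial, and the sample size of 44 is right for its own inputs. With equal completers there is no bias and the test is conservative. A biased estimate needs both a period effect and unequal completers.

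The size rests on an assumed δ. At 0.25 with 22/22 completers the term is worth about 1 power point under either reading; at 0.5 it is worth about 5 points (A) or 3 points (B). Because the cost is so small, the change is worth making even if a period effect is only possible.

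**What to change.** Before unblinding, write the primary model in section 11.4.2 as: outcome ~ condition + period (first versus second treatment period) + sex + age + random subject. Add the same period term to the behavioural secondary models, next to acute versus repeated administration, and to the rMT model so that it still matches the primary. Report the number of completers by sequence.

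The cost is one line of text and one degree of freedom in the primary model. If there is no period effect, the power lost is 0.03 points at 22/22, 0.3 at 24/20 and 0.6 at 25/19. No new data or participants are needed. Timing matters: a period term added after unblinding would be a data-dependent choice.

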11.4.1 Datasets to be analyzed, analysis populations

We will apply a Per-Protocol-Analysis, i.e. the analysis of the primary and secondary outcome measures will be only performed with those participants, who completed all tests and investigations. There will be replacement of Drop-Outs until data of 44 participants are completed. Drop-Outs will be thoroughly described to assess the reason(s) for dropping out.

We will recruit up to 4 subjects more towards the end of the trial to prevent under-recruitment due to Drop-Outs. If more than 44 subjects will complete all tests and investigations their data will also be analyzed.

